10.4 Theoretical Assessments

Theoretical assessments will include descriptive and regression models to explore PrEP cascade level and constructs of the UTAUT2. We will add UTAUT2 constructs as independent variables to the above specified GEE models. Analyzing constructs of the UTAUT2 model will allow for estimation of structural equation modeling coefficients to inform assessment of required sample size to determine theoretical components of an eventual SEM in a future RCT of the intervention (Aim 4). Analysis will also inform our understanding of whether the theoretical model is appropriate for capturing pathways of the intervention effects. Process outcomes will be reported with descriptive statistics.

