6.0 MEASURES

A summary table of study measures, and sources for each measure, are provided in the table below. Measurement of tenofovir-diphosphate (TFV-DP) levels will be conducted using liquid chromatography/tandem mass spectrometry methods on DBS samples. TFV-DP level can be translated to an interpretation that indicates mean number of days per week PrEP is ingested over a period of approximately one month. The cutpoint used will be TFV-DP levels considered a surrogate for substantial protection: >700 fmol/punch, a level indicating >4 doses/wk.

Construct	Measure	Data source	Definition	Analysis
PRIMARY OUTCOMES				
Feasibility	Home HIV test orders	Order fulfillment	Proportion of participants sent a home HIV test	Benchmark ≥ 30%
Feasibility	Condom orders	Order fulfillment	Proportion of participants sent 'choice' condom package	Benchmark ≥ 30%
Feasibility	PrEP initiation	Clinical site data	Proportion of participants receiving a PrEP prescription	Benchmark ≥ 20%
Acceptability	Systems Usability Scale ^{126, 127}	Survey	10-item scale, good score is >71	Benchmark: Good score (≥ 71 out of 100)
Acceptability	Ratings for intervention components ⁷²	Survey	Likert acceptability rating for each intervention component (e.g. home HIV test)	Benchmark: Acceptable ratings (≥ 3 out of 5)
PRELIMINARY EFFICACY ASSESSMENT				
HIV testing	HIV testing ^{44,128}	Survey	Change in median number HIV tests	GEE model
Condom use	Condom use ^{44,128}	Survey	Change in proportion of participants reporting always using condoms for anal sex	GEE model
PrEP Use	PrEP use ¹²³⁻¹²⁵	Laboratory data	Number participants with protective levels of TDF-DP	Descriptive report
THEORETICAL ASSESSMENT				
Prevention cascade	PrEP cascade levels ¹²⁹	Survey and clinical site data	PrEP awareness, willingness, prescription, persistence in care, and medication adherence	Descriptive and logistic regression
Theoretical assessment	Unified Theory of Acceptance and Use of Technology (UTAUT2) ¹²¹	Survey	Validated items for performance expectancy, effort expectancy, social influence, hedonic motivation, and habit.	Descriptive and GEE model to estimate SEM parameters
PROCESS OUTCOMES				
Process	New HIV testers	Survey	Proportion changing from never to ever HIV test	Descriptive report
Process	New condom users	Survey	Proportion changing from none to some condom use	Descriptive report
Process	Visits to local health clinics	Survey	Proportion receiving HIV services at health departments	Descriptive report

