10.2 Power to Detect Effects in Primary Outcome

This is a feasibility pilot and therefore is not powered to detect significant differences relative to the baseline period. The use of a non-powered pilot design is called for by the MP3 mechanism. A sample of 200 individuals per intervention city was selected based on what was determined to be achievable given budget and time constraints. It is also anticipated that this number will provide estimates of key parameters with sufficient precision. For instance, the prevalence of our binary benchmarks (home HIV

test orders, PrEP initiation) would be estimable with the following 95% confidence intervals half-width at specified prevalences: $20\% \pm 4\%$; $30\% \pm 5\%$; $50\% \pm 5\%$.

Led by the study statistician, additional analyses will be conducted to assess (1) preliminary efficacy with endpoints measuring change from baseline to intervention periods in HIV testing, condom use, and PrEP use, (2) theoretical efficacy with endpoints in the PrEP cascade and UTAUT2 constructs, and (3) process outcomes with endpoints of new HIV testers, new condom users, and app use metrics. These assessment will leverage the pilot's interrupted time series design and inform future clinical trial design.

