10.3 Preliminary Efficacy Assessment

Preliminary efficacy assessments will describe differences in outcomes for the intervention, compared to the baseline period, for the median number of HIV tests and the proportion reporting all anal sex acts as condom-protected. A generalized estimating equations (GEE) repeated measures analysis will be conducted for the binary outcome of HIV testing (test/not testing). The GEE model will contain the seven time periods with primary comparisons of 0-month (first baseline) measurement to 6-month (end wash-out baseline period measurement and to 12-month (end first intervention period) measurement. Time will be considered as a fixed effect to compare proportion tested across intervals, with a random intercept for individuals. A similar GEE model will be conducted for the condom outcome (always/not always condom use). Logistic regression models will be fitted to understand PrEP cascade progressions, with the main analysis being any forward progress (yes/no) in the overall cascade between 0-month and 15-month measurements. These analyses will consider variables of progression in the PrEP cascade. Time at which cascade progress was made (e.g. 3 months) will be entered as a co-variate. A multifaceted approach to address missingness for our outcomes will be used. Primary analyses will treat values as missing at random. Sensitivity analyses will re-analyze data using both last-value-carried-forward and multiple imputation methods.

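### Adding UTAUT2 scores as predictors in the 10.3 GEE models does not estimate the structural equation parameters that 6.0 and 10.4 promise for Aim 4

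*Combined protocol and SAP*

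**What the plan says.** Section 10.3 sets out two GEE models over the survey visits, one for HIV testing (yes/no) and one for condom use (always/not always). Time is a fixed effect, and the main comparisons run from month 0 to months 6 and 12.

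Section 10.4 then states: "We will add UTAUT2 constructs as independent variables to the above specified GEE models". It continues: "Analyzing constructs of the UTAUT2 model will allow for estimation of structural equation modeling coefficients to inform assessment of required sample size". The sample size in question is that of an eventual SEM in a future randomised trial, under Aim 4. The UTAUT2 row of the measures table in 6.0 gives the analysis as "Descriptive and GEE model to estimate SEM parameters" and lists what is measured as "Validated items for performance expectancy, effort expectancy, social influence, hedonic motivation, and habit".

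Two further statements bear on the role of the constructs. Section 10.2 lists "theoretical efficacy with endpoints in the PrEP cascade and UTAUT2 constructs", so there they are outcomes. Section 10.4 also wants to learn "whether the theoretical model is appropriate for capturing pathways of the intervention effects", which places them between the intervention and behaviour.

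The plan does not say at which surveys the UTAUT2 items are asked, whether they refer to Blued or Blued+, or whether scores enter the models as time-varying or person-level covariates.

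**The concern.** An SEM has two parts: a measurement model linking items to latent constructs, and a set of equations in which constructs can be both outcomes and predictors. The planned GEE has neither. It is one regression of a behaviour on observed scores. If its slopes are carried into Aim 4 as SEM coefficients, the future SEM would be sized on quantities of a different kind. The parameters that drive such a calculation (loadings, covariances among constructs, the effect of the intervention on each construct) would still be unknown after the pilot.

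A secondary issue is that the constructs are added to the same models that carry the month-0 comparison. A construct that responds to Blued+ lies on the pathway of the effect. Once it is in the model, the time coefficient no longer measures the total change from baseline.

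**Working it through.** The plan gives no SEM coefficient, reliability or sample size for this analysis, so there is no stated figure to reproduce. The check first compares what is promised with what is fitted, and then uses simulation to show size.

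**1. What the GEE supplies and what an SEM needs.** The table in 6.0 names five constructs.

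| Quantity | Augmented GEE | SEM with five correlated constructs |
|---|---|---|
| Construct-to-behaviour slopes, per outcome | 5, on observed scores | 5, on latent constructs |
| Covariances among constructs | 0 | 5 × 4 / 2 = 10 |
| Period-to-construct paths | 0 | 5 |
| Indirect effects via single constructs, per outcome | 0 | 5 |
| Item loadings | 0 | at least one set per construct (item count not stated) |

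No other analysis in sections 6.0 or 10 supplies the missing rows. No measurement model, no equation with a construct on the left-hand side and no indirect-effect estimator is specified.

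**2. Size of the measurement-error effect.** All simulation values are assumptions. There were six visits, a logistic GEE with exchangeable working correlation and time as a factor. One unit-variance construct had a log-odds effect of 0.6, the direct period effect was 0.2, the construct rose by 0.8 SD once Blued+ was available, and there were 10,000 participants per run. Loss = 1 − (slope on observed score / slope on error-free construct).

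| Reliability | Error-free slope | Observed-score slope | Loss |
|---|---|---|---|
| 0.7 | 0.544 | 0.348 | 1 − 0.640 = 36% |
| 0.8 | 0.528 | 0.400 | 1 − 0.758 = 24% |
| 0.9 | 0.547 | 0.478 | 1 − 0.874 = 13% |

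This is a one-construct check. With five correlated scores, error in one also leaks into the slopes of the others, so the bias in any single slope is harder to predict.

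**3. The time coefficient in a construct-adjusted model.** The result depends on details the plan leaves open.

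- *Items asked only once Blued+ exists.* With complete data there are 400 × 6 = 2,400 rows, of which 400 × 4 = 1,600 remain. The 800 lost (33%) include every month-0 and month-3 row, so a month-0 contrast cannot be estimated in that model.
- *Items asked at every survey, scores time-varying.* The month-12 versus month-0 log-odds, at reliability 0.8 and with 20,000 participants, were:

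| Assumed shift in construct | Without construct | With construct |
|---|---|---|
| 0.8 SD | 0.592 | 0.294 |
| 0.4 SD | 0.354 | 0.215 |
| none | 0.180 | 0.192 |

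- *One post-launch score per person.* At a 0.8 SD shift, 0.592 becomes 0.601 (month-15 score) or 0.610 (mean of months 6 to 15), so there is no material change.

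**The case against.** Several points can be made for the plan. The theoretical assessment is exploratory, the pilot is openly unpowered, and 10.4 promises only to inform a later sample size calculation. A GEE slope is not worthless for that: in a path model on observed variables it can serve as a rough stand-in for one direct path. The 6.0 entry also includes descriptive analysis, under which score correlations could be reported. All of this limits the consequence. It does not make the claim true, because both sections name the GEE as the means of getting SEM parameters, and observed-score summaries are not loadings or structural paths.

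A reader might go further and infer that the before/after comparison itself is lost or distorted. The documents do not support that. The 10.3 models are specified without constructs, and nothing in 10.4 replaces them or reports the construct-adjusted time coefficient as efficacy. The existing Blued app is available at months 0 and 3 (5.2), so baseline answers are possible. As shown above, a person-level score, or constructs that do not move, leaves the contrast essentially unchanged.

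A reader might also conclude that the UTAUT2 analysis should be confined to months 6 to 15. That would discard any baseline scores, which are what a period-to-construct path needs and what the interrupted time series design in 10.2 is meant to exploit.

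**Conclusion.** The concern holds for the SEM claim. Sections 6.0 and 10.4 attribute to the augmented GEE a property it does not have. It yields five observed-score slopes per outcome, weakened by measurement error, and none of the loadings, covariances, construct-as-outcome paths or indirect effects. This follows from the form of the model and needs no assumption. The 13% to 36% loss is illustrative and rests on assumed reliabilities of 0.7 to 0.9 and a single construct.

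On the baseline contrast the conclusion is conditional. Within the construct-adjusted models, the month-0 comparison disappears if items are asked only after launch, and shrinks if time-varying scores rise with Blued+ (by about half at an assumed 0.8 SD shift). Otherwise it is unaffected. The 10.3 estimate stands in every case.

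The consequence is confined to exploratory analyses and the planning of the future trial. The primary feasibility and acceptability benchmarks are untouched.

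**What to change.** - In 10.4 and the UTAUT2 row of 6.0, replace the GEE as the source of SEM parameters with a confirmatory factor and path model on the UTAUT2 items. It should use participant-clustered standard errors and a link suited to binary outcomes. Report loadings, construct covariances and paths with confidence intervals as the inputs to Aim 4.
- Keep the construct-augmented GEE only as a description of association.
- State that the before/after estimate comes from the 10.3 models without constructs, and that the time coefficient in a construct-adjusted model is not an efficacy estimate.
- State at which surveys the items are asked, about which app, and how scores enter. If baseline scores are collected, use them for the period-to-construct path and do not limit the analysis to months 6 to 15.

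The cost is SAP wording and a modest amount of extra analysis on survey items already planned. No change to recruitment, visits or the intervention is needed. With about 400 participants some paths will be imprecise, and the intervals should be carried into the Aim 4 calculation.

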App use	Time spent in health portal	App paradata	Hours of app health portal exposure	Descriptive report
App use	Consistency of use over time	App paradata	Number with monthly visits to health portal	Descriptive report

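### The UTAUT2 analysis leaves out use of Blued+, so it cannot separate the two links that the pathway aims in section 10.4 depend on

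*Combined protocol and SAP*

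**What the plan says.** The measures table in section 6.0 gives the theory its full name, "Unified Theory of Acceptance and Use of Technology (UTAUT2", and lists five groups of survey constructs, one of them habit. The analysis column there mentions a GEE model to estimate structural equation parameters but names no outcome.

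Section 10.4 supplies the missing detail: "We will add UTAUT2 constructs as independent variables to the above specified GEE models". The models above it, in section 10.3, are a GEE in which a "repeated measures analysis will be conducted for the binary outcome of HIV testing (test/not testing"), and a second one: "A similar GEE model will be conducted for the condom outcome". PrEP cascade progress is analysed by logistic regression, so the sentence about GEE models does not reach it.

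App use has two rows in section 6.0, both from app paradata. One is defined as "Hours of app health portal exposure"; the other counts men with monthly portal visits. Both are marked for descriptive reporting. Section 10.2 classes app use as a process outcome, and section 10.4 says: "Process outcomes will be reported with descriptive statistics".

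Section 10.4 gives the analysis two purposes. It is to yield structural equation coefficients for sizing a future trial (Aim 4), and to inform a view on "whether the theoretical model is appropriate for capturing pathways of the intervention effects".

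**The concern.** Section 5.3 makes Blued+ the main part of the intervention that participants see, so a plausible route from acceptance of the app to behaviour runs through using it: construct to use, then use to HIV testing or condom use. No planned model has app use as an outcome of the constructs, as a predictor of behaviour or as a mediator.

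A construct coefficient in the HIV-testing model then has no single interpretation. If it is near zero, the construct may not drive use, use may not drive testing, or both links may hold with a product too small to see. If it is clearly non-zero, its split between the two links is still unknown. Aim 4 would receive an estimate of neither link, although section 10.4 intends the pilot to supply such parameters.

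**Working it through.** **1. Tracing the models.**

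| Quantity | Role in the plan | Section |
|---|---|---|
| HIV testing (yes/no) | GEE outcome; receives UTAUT2 constructs | 10.3, 10.4 |
| Always-condom use (yes/no) | GEE outcome; receives UTAUT2 constructs | 10.3, 10.4 |
| PrEP cascade progress | Logistic regression; no stated role for the constructs | 10.3, 10.4 |
| Portal hours, monthly visits | Described only | 6.0, 10.2, 10.4 |

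Section 7.4 records every button touch under an ID unique to the participant, so person-level use will exist.

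**2. The plan's own figures.** Section 10 gives no precision for the UTAUT2 analysis. Its only precision figures are 95% half-widths for the binary benchmarks. With n = 400 the Wald formula gives 1.96 × √(0.2 × 0.8/400) = 3.92 points at 20%, 4.49 at 30% and 4.90 at 50%, close to the stated 4, 5 and 5. They do not bear on this point.

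**3. Why the total cannot be split.** Under full mediation with standardised paths a (construct to use) and b (use to behaviour), the construct-to-behaviour association is a × b. The sample size for 80% power at two-sided 5% is N = ((1.960 + 0.842)/atanh(r))² + 3. All path values are assumed.

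| a | b | a × b | N for a | N for b | N for the total |
|---|---|---|---|---|---|
| 0.50 | 0.30 | 0.15 | 30 | 85 | 347 |
| 0.30 | 0.50 | 0.15 | 85 | 30 | 347 |
| 0.25 | 0.60 | 0.15 | 124 | 20 | 347 |
| 0.60 | 0.25 | 0.15 | 20 | 124 | 347 |

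The planned models see the same 0.15 in every row, yet the rows say different things about the theory and imply different path sample sizes. With app use as an outcome the pilot could tell the first two apart: at n = 400 the 95% interval, tanh(atanh(r) ± 1.96/√397), is 0.42 to 0.57 for r = 0.5 and 0.21 to 0.39 for r = 0.3.

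**4. Size, as an illustration.** Assume full mediation, a correlation of 0.3 between construct and use, an odds ratio of 1.5 per SD of use, about 28% testing, and n = 400 at one survey.

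- Implied construct log odds ratio: 0.3 × ln 1.5 = 0.3 × 0.405 = 0.122.
- Approximate standard error: 1/√(400 × 0.28 × 0.72) = 0.111.
- z = 0.122/0.111 = 1.09, so power is about Φ(1.09 − 1.96) = Φ(−0.87) = 19%. Simulation also gives about 19%.
- Use-to-testing link, adjusted for the construct: standard error 0.111/√(1 − 0.09) = 0.117, z = 0.405/0.117 = 3.47, power about Φ(1.51) = 93%.
- Construct-to-use link: z = atanh(0.3) × √397 = 6.2, power close to 100%.
- Both links together: about 91% by simulation.

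Other single-survey settings, by simulation:

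| Correlation | Odds ratio | n | Construct on testing | Both links |
|---|---|---|---|---|
| 0.3 | 1.5 | 320 (assumed 20% loss) | 16% | 84% |
| 0.3 | 1.7 | 400 | 28% | 99% |
| 0.2 | 1.5 | 400 | 11% | 92% |

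The planned GEE pools surveys. With four intervention-period surveys, an exchangeable GEE and an assumed person random-intercept SD of 1, the base setting rises from about 19% to about 36% with the construct fixed over time, and to about 46% if half its variance is within person. At a correlation of 0.2 the range is about 15% to 19%. These rest on 150 replicates; at 36% the Monte Carlo standard error is √(0.36 × 0.64/150), about 4 points. No four-survey figure was computed for the two-link approach, so 36% and 91% are not a like-for-like pair.

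**The case against.** Much of the case on the other side stands.

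- **Other uses of the constructs.** Section 10.4 opens by mentioning regression models that explore PrEP cascade level and the UTAUT2 constructs, and section 10.2 lists the constructs among its endpoints. A reader might infer that the constructs are examined only against HIV testing and condom use, and that goes too far. What holds is that these are the only models specified with the constructs as predictors. Neither sentence brings in app use.
- **The choice of outcome.** A reader might infer that the dependent variable is wrong for this theory. Only the theory's name points that way; the documents do not set out its structure. Relating acceptance of an app to the behaviours it targets is a legitimate exploratory question. The analysis is incomplete, not wrong.
- **The consequence.** A reader might infer that a null coefficient would cause the theory to be dropped. No such decision rule exists. Section 10.4 speaks of informing understanding and leaves the structural equation model to a future trial.
- **The power contrast.** A reader might take the one-survey percentage as the power of the planned analysis. It is not, because pooling surveys raises it. Full mediation, no confounding and perfectly measured use also favour the two-link approach, and section 10.2 says the pilot is not powered for differences from baseline.
- **The remedy.** The use-to-behaviour link is observational. Habit may overlap with use. App data and surveys sit under IDs whose linkage to each other is not described (sections 7.3 and 7.4); the explicit linkage statement in section 5.3.1 concerns PrEP clinic visits.

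None of this closes the gap: no planned model separates the two links, and pooling surveys does not do so either.

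**Conclusion.** The point holds as a gap in specification. The GEEs for HIV testing and condom use are the only models specified with UTAUT2 constructs as predictors, and app use is only described. The planned analysis therefore cannot estimate either link in the pathway that section 10.4 says it will inform. This conclusion comes from the text and from the identity total = a × b, and it needs no power argument.

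The percentages show only how much weaker the product can be than its parts. They depend on assumed effect sizes, full mediation and an assumed within-person correlation, none of which is in the documents. The effect is confined to the theoretical assessment and to what it passes to Aim 4. The feasibility and acceptability benchmarks are untouched.

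**What to change.** In section 10.4, keep the planned GEEs and the app-use descriptives, and add two sets of exploratory models.

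1. **Constructs to use.** For months 6 to 15, take app use (monthly portal visit yes/no; portal hours) as the outcome of the UTAUT2 constructs, shown with and without habit.
2. **Use to behaviour.** Relate HIV testing and always-condom use to app use in the preceding quarter, adjusted for the man's pre-intervention level. The intervention starts at month 3, so state which survey is the first with a preceding quarter of use.

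Report both links with 95% intervals and call them associations. State how the paradata ID is joined to the survey study ID. If the models are not added, withdraw the statement about pathways.

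The cost is some wording, a linkage step and two sets of regressions on data the study will already hold. The drawback is that the second link may reflect motivation rather than an effect of use, which is why it must be labelled exploratory.
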